Cover Page for Protocol

Sponsor-Investigator:	[name]
NCT Number:	NCT03597568
Unique Protocol ID:	201806073
Official Title:	Effect of resveratrol on endothelial function in patients with CKD and diabetes: A randomized controlled trial
Document Date:	23 February 2024

Background and significance

Patients with chronic kidney disease (CKD) have an exceptionally high risk for cardiovascular disease (CVD) and are 10 times more likely to die from CVD prior to requiring dialysis or kidney transplantation (1). Multiple studies have shown CKD to be an independent risk factor for cardiovascular events and mortality (2-6). Diabetes mellitus is the most common cause of CKD and is believed to contribute to a significant portion of the CVD with CKD (7). Indeed, patients with CKD and diabetes have a disproportionately higher risk for CVD when compared with patients with diabetes who do not have CKD (8). Thus, it is paramount that we explore therapies that may ultimately reduce the burden of CVD in those with CKD and diabetes.

Endothelial dysfunction via brachial artery flow mediated dilation (BA-FMD), is a reliable and non-invasive vascular assessment, which has been shown to predict CVD *prospectively* in a wide variety of 'at-risk' and diseased populations, including individuals with CKD (9). Preliminary data by our group demonstrates that endothelial function via BA-FMD test is significantly lower in individuals with CKD and diabetes as compared to those with CKD but without DM (Fig 1). These findings suggest that the etiology of DM within CKD patients appears to exacerbate the condition more so than CKD alone.

Experimental studies, suggest that resveratrol (a widely-available nutraceutical) inhibits inflammation and restores endothelial nitric oxide (NO) *in vitro* (9-11) and *in vivo* (12,13).

In this pilot study, we will evaluate if resveratrol supplementation improves endothelial function and oxidative stress in those with CKD and diabetes.

Study Design

25 subjects with stage 3 CKD and diabetes will be randomized to receive either resveratrol first then matching placebo or placebo first then resveratrol in a randomized cross over study. Resveratrol will be prescribed at 400 mg per day. The treatment with resveratrol or placebo will be for 6 weeks and separated by a 2 week washout period.

The inclusion criteria are shown in Table 1.

Figure 1: Patients with DKD exhibit lower BA-FMD compared to those with CKD without diabetes

[figure not shown]

Table 1

Inclusion Criteria	Exclusion Criteria
Age 45-80 years old	Consuming >2 glasses/day red wine and/or taking resveratrol or vitamin C supplement in the past 12 months
CKD stage 3 (CKD-EPI eGFR: 30-60 mL/min/1.73m ²) on 2 occasions \geq 3 months apart	Life expectancy <1 year
Type II DM	Pregnant, breastfeeding, or unwilling to use adequate birth control
angiotensin converting enzyme inhibitor or angiotensin II receptor blocker for \geq 3 months prior to the study	Uncontrolled hypertension; blood pressure >140/90
Able to give informed consent	Severe liver disease
	Severe congestive heart failure
	Hospitalization within the last 3 months
	Active infection or antibiotic therapy
	Immunosuppressive therapy within the last year
	Uncontrolled DM with A1C > 8.5
	Currently taking anticoagulants including the following: coumadin, dalteparin, enoxaparin, heparin, and plavix.
	Severe systolic heart failure
	Currently partaking in another research study

Our rational for RSV dose is that: 1) it is available commercially at 400 mg and 2) recent studies utilizing RSV suggest that this dose is safe and does not result in serious side effects (14, 15).

The study is registered with clinicaltrials.gov

Institutional Review Board was obtained. The informed consent will detail the risks associated with the study drug and with all the study procedures.

- **Detailed study sessions**

All study procedures will be conducted at UIHC Clinical Research Unit (CRU) and all experimental testing measurements will be conducted after an overnight fast as well as refraining from exercise and caffeine prior to testing.

Session 1: Informed consent and screening questionnaire for inclusion and exclusion criteria including confirmation of stage 3 CKD on 2 separate occasions in the last 6 months. All women in child-bearing age will undergo pregnancy test at this visit. In addition, all participants will complete a 7-day physical activity recall.

Session 2:

- Blood pressure at rest
- Endothelial cell sampling
- Blood sampling for fasting lipid profile
- Blood sampling for hemoglobin A1C
- Blood sampling for levels of RSV and its metabolites
- Blood sampling for basic metabolic profile and estimated GFR including cystatin C
- Blood sampling for circulating markers of inflammation and oxidative stress (oxLDL)
- Urine sampling (random) for albumin/creatinine ratio (ACR)
- Evaluation of EDD and EID by measurements of BA-FMD and nitroglycerin-mediated dilation (NMD)
- Start study drug after this visit

Session 3: will include the same measurements as Session 2. In addition, it will include the following:

- Physical activity questionnaire
- Pill count
- Safety monitoring:
 - Completion of an adverse event questionnaire
 - Update medication list

Sessions 4 and 5: will involve the exact same procedures as Sessions 2 & 3 above except it will involve the other study drug being ingested for 6 weeks (resveratrol or placebo).

- **Outcome measurements**

1. Measurements of endothelial dependent and independent dilation: *Endothelial dependent dilation* (EDD) of the brachial artery (BA-FMD) will be measured at the Cardiovascular Research Lab in the Clinical Research Unit (CRU) at the University of Iowa by principal investigator using high-resolution Doppler ultrasonography as described originally by Celermajer et al (16,17). *Electrocardiogram (ECG) gated end-diastolic ultrasound images and Doppler flow of the artery will be acquired during baseline and FMD and conditions.* Briefly, and after 15 minutes of quiet supine rest, the vascular reactivity of the brachial artery will be assessed as based on the following: 1) two minutes of baseline hemodynamics followed by inflation of a rapidly inflating pneumatic pediatric cuff wrapped around the maximal circumference of the forearm to a pressure of 240 mmHg for 5 min, and 2) rapid deflation of the cuff after five minutes. A commercially available software package will be used to acquire and analyze ECG-gated brachial artery diameters. *Endothelial independent dilation (EID) will also be determined by measuring brachial artery dilation for 10 minutes after administration of sublingual nitroglycerin (0.4 mg).* BA-FMD

(pre- vs. post-intervention) will be calculated as the % change from baseline and compared against the placebo condition.

2. Systemic markers of oxidative stress: oxidized low density lipoprotein (LDL) cholesterol (ALPCO Diagnostics, Catalog #30-7810) will be quantified using commercially available enzyme-linked immunosorbent assays performed according to kit instructions.

3. Endothelial cell sampling and cell protein expression: This technique will be done by a trained/qualified individual at the UI CRU. Briefly, J-wires will be advanced into an antecubital vein and withdrawn. Cells will be recovered by standard techniques (18). Collected cells will be fixed with 3.7% formaldehyde and plated on slides. After blocking nonspecific binding sites with 5% donkey serum, cells are incubated with the primary antibody and with CY3-conjugated secondary antibodies. Slides will be systematically scanned to identify endothelial cells (positive VE-Cadherin) and nuclear integrity confirmed using 4',6'-diamidino-2-phenylindole hydrochloride staining. Once endothelial cells with intact nuclei are identified, images will be captured and then analyzed to quantify the intensity of CY3 staining (i.e., average pixel intensity). Values for each sample will be reported as ratios of endothelial cell protein expression/human umbilical vein endothelial cell (HUVEC) to account for any variation in the staining procedure. Sirtuin 1 expression will be evaluated since this has been reported to increase with resveratrol.

4. Other measurements: High performance liquid chromatography coupled with tandem mass spectrometry will be used to determine plasma and urine levels of resveratrol and its metabolites. In addition, urinary albumin/creatinine ratio, serum creatinine and estimated GFR will be assessed at the University of Iowa Clinical Lab.

- **Statistical analysis**

Normally distributed data are presented as mean \pm SD, non-normally distributed data as median (interquartile range), and categorical data as count (percentage of patients). To determine the effects of resveratrol supplementation on our primary and secondary outcomes, a generalized linear mixed effects model was used to examine the significance of condition, time, and their interaction for normally distributed variables, and a gamma mixed effects model was used for non-normally distributed variables. In each model, a random intercept was built for each patient to account for inherent between-patient variability. A complete case analysis was utilized when analyzing primary and secondary outcomes. A Wilcoxon Rank Sum Test was used to test differences in resveratrol metabolites between the resveratrol and placebo arms. Significance was set at an alpha level of 0.05. All analyses were performed in R, version 4.2.3 (R Foundation for Statistical Computing, Vienna, Austria).

References

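### Minor safety gap: the only listed pregnancy test is at screening, nominally at least 8 weeks before the second study drug starts, and no retest is listed

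*Combined protocol and SAP*

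**What the plan says.** Under Detailed study sessions, Session 1 covers consent and screening and includes the only pregnancy test: "All women in child-bearing age will undergo pregnancy test at this visit". Table 1 admits patients at "Age 45-80 years old" and excludes those who are "Pregnant, breastfeeding, or unwilling to use adequate birth control". It also excludes current infection or antibiotic use, and a list of anticoagulants.

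Session 2 lists blood pressure, endothelial cell sampling, blood and urine samples, and the brachial artery measurements. It ends with "Start study drug after this visit". Session 3 "will include the same measurements as Session 2. In addition, it will include the following": a physical activity questionnaire, a pill count, and two safety items, "Completion of an adverse event questionnaire" and "Update medication list". Sessions 4 and 5 are described only by reference. The text says that this part "will involve the exact same procedures as Sessions 2 & 3 above", with the other study drug.

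Study Design gives 6 weeks on each treatment and 2 weeks of washout between them.

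**The concern.** A crossover has two drug starts. The protocol treats pregnancy, infection and certain medicines as reasons not to enter, and it orders a pregnancy test before the first start. The session lists do not repeat that test before the second start. For patients randomized to placebo first, the second start is when they first take resveratrol, so the only listed test precedes their first active dose by about two months or more.

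A related question is whether anyone asks about new illness or new medicines at Session 4, before a wire is advanced into a vein again and the second drug is handed out. The answer depends on how the one-sentence description of Sessions 4 and 5 is read.

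What is at stake is participant safety at one visit, and at most the occasional loss or delay of a patient's second period.

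**Working it through.** The plan gives no figure of its own on this point. The check consists of the visit timeline, a reading of the session lists, and a rough size.

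**Timeline.** Take Session 2 as week 0 and let g ≥ 0 be the unstated gap in weeks from Session 1 to Session 2. No visit windows are given, so these are nominal values.
- Session 3, end of period 1: week 6.
- Session 4, second drug start: 6 + 2 = week 8.
- Session 5, end of period 2: 6 + 2 + 6 = week 14.
- Pregnancy test to second drug start: g + 8, so at least 8 weeks. Test to end of second drug: g + 14, so at least 14 weeks.

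**Is a retest listed on any reading?** The Session 2 list has no pregnancy test. Session 3 takes over the Session 2 measurements and adds four items, none of them a pregnancy test. Sessions 4 and 5 take their content from Sessions 2 and 3, so they contain none either, however the two pairs of visits are matched.

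**Is there an adverse event or medication check at Session 4?**
- *Paired reading (4 = 2, 5 = 3).* The drug start belongs to Session 2 and the pill count to Session 3. A pill count after a washout would make little sense, so this reading is the more natural one. The last check before the second start is then Session 3, 8 − 6 = 2 weeks earlier. The next is Session 5, after J-wire sampling and 6 weeks of dosing.
- *Joint reading (4 and 5 each carry all procedures of 2 and 3).* Session 4 then includes both checks, and only the pregnancy part remains.

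**Size, pregnancy.** The documents give no split by sex or by age within the 45-80 range. Assume 40-60% women, 5-20% of them of child-bearing age, and 0.1-1% conceiving over 8 weeks.
- Women tested: 25 × 0.40 × 0.05 = 0.5 to 25 × 0.60 × 0.20 = 3.0.
- Expected pregnancies: 0.5 × 0.001 = 0.0005 to 3.0 × 0.01 = 0.03.
- Placebo-first half, assuming an equal split: 0.00025 to 0.015.

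**Size, infection or antibiotics in the washout.** Assume 0.25 to 1 episode per patient-year.
- Episodes starting: 25 × (2/52) × 0.25 = 0.24 to 25 × (2/52) × 1 = 0.96 in the whole trial. Fewer would still be active at Session 4.

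**Cost of a lost second period.** 1/25 = 4% of within-patient pairs for each patient.

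**The case against.** The strongest case against raising this is that the consequence is close to nil. Patients are at least 45, women unwilling to use birth control are excluded, and that criterion looks forward over the treatment interval. Screening plus contraception is a defensible choice. This stands, and it is why the point is minor. It does not change the fact that a safeguard the protocol chose to use is not listed again at the second drug start.

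Further objections limit what can be said, and each of them holds:
- A reader might infer that Session 4 has no safety check at all. The text does not support that without a condition, because on the joint reading both checks are there. Even on the paired reading Session 3 had them 2 weeks before, and Session 4 still repeats blood pressure and laboratory tests. Those tests are no substitute for asking about illness and medicines.
- A reader might infer that the protocol breaks its own eligibility rules. It does not. Table 1 sets entry criteria, and nothing requires them to be confirmed again before period 2.
- A reader might infer a fetal hazard, or bias in the primary outcome. The documents describe no pregnancy hazard of resveratrol, and nothing here bears on BA-FMD.
- A reader might extend the point to Session 2. That visit follows screening at an interval the text does not give, so the documents do not show a gap there.
- Instructions to report pregnancy, illness or new medicines may be in the consent form, which is not part of the text reviewed. The point is therefore limited to the session lists.

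Finally, the Statistical analysis section is written in the past tense, so an amendment may come too late.

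**Conclusion.** The point holds as a cheap safety improvement of minor priority. It is not an error in any stated rule or figure. The absence of a listed pregnancy retest, nominally 8 weeks or more after the only test, holds on every reading of Sessions 4 and 5. The absence of an adverse event and medication check at Session 4 holds only if Session 4 mirrors Session 2.

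The expected number of pregnancies is near zero. A washout infection or antibiotic course is less remote, at no more than about one in the whole trial. Both sizes rest on the assumed rates above, since the documents give none.

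**What to change.** Spell out Session 4 instead of defining it by reference. Before J-wire sampling and dispensing, all participants repeat the Session 3 adverse event questionnaire and medication update. Women of child-bearing age have a urine pregnancy test on the random sample already taken for the albumin/creatinine ratio, so that sample must be collected first. State what follows from each result:
- Positive pregnancy test: the second drug is not started.
- Active infection or antibiotic course: sampling and dosing are deferred until it has resolved.
- Newly started anticoagulant: the investigator decides whether to proceed and documents the decision.

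Do not re-apply the blood pressure or A1C entry thresholds. That would remove randomized patients from a 25-patient crossover analysed by complete cases.

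The cost is a short amendment, test strips for about 0.5 to 3 women (assumed range), and a few minutes of an existing questionnaire per patient. The downside is a rare patient whose second period is delayed, which only lengthens that patient's washout, or lost, which costs 4% of pairs each time.

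If dosing has ended, one or two sentences in the report are enough: that pregnancy was tested only at screening, if that is what was done, and which adverse event and medication checks took place at Session 4.

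### No safety contact is specified after Session 5, and no adverse event questionnaire is listed at the end of the washout, so neither off-drug interval has its own inquiry

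*Combined protocol and SAP*

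**What the plan says.** Study Design in the combined protocol and SAP sets out a two-sequence crossover: "25 subjects with stage 3 CKD and diabetes will be randomized to receive either resveratrol first then matching placebo or placebo first then resveratrol". On timing it says: "The treatment with resveratrol or placebo will be for 6 weeks and separated by a 2 week washout period".

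Detailed study sessions gives the visit content. Session 2 is the pre-treatment visit, with blood pressure, endothelial cell sampling, blood and urine tests (including renal function) and the vascular tests. It ends with the instruction "Start study drug after this visit". The next entry reads "Session 3: will include the same measurements as Session 2. In addition, it will include the following", and the additions are an activity questionnaire, a pill count and safety monitoring. Safety monitoring consists of "Completion of an adverse event questionnaire" and an update of the medication list. The second period is defined by reference to the first: "Sessions 4 and 5: will involve the exact same procedures as Sessions 2 & 3 above except it will involve the other study drug being ingested".

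Outcome measurements describes two procedures that recur at every session from 2 to 5. One is the endothelial cell sampling, in which "J-wires will be advanced into an antecubital vein and withdrawn". The other is a 0.4 mg sublingual nitroglycerin challenge.

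The session list then ends. It gives no later visit or call, no recall period for the questionnaire, and no rule for following unresolved events or abnormal results. Statistical analysis does not mention adverse events.

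**The concern.** A questionnaire completed at the same visit as the last procedures cannot pick up what happens after the patient leaves. It also cannot pick up anything that appears once the second drug has been stopped. A site that followed the session list exactly would never ask about either.

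The washout has a related problem. Session 4 copies Session 2, which has no questionnaire. The next inquiry after Session 3 is therefore Session 5, when the patient has been on the other drug for about 6 weeks. An event that began off drug after the first treatment may go unrecalled, or may be recorded against the second. In a crossover, that moves an event from one treatment column to the other.

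What is at stake is the completeness and attribution of the safety record, in patients who all have stage 3 CKD and diabetes.

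**Working it through.** The plan gives no safety figure to reproduce, so this is a check of the schedule.

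**Inputs.** 25 patients, 6 weeks per treatment and a 2-week washout (Study Design). Drug starts after Session 2 and, by the copying rule, after Session 4; the questionnaire is listed under Session 3 only (Detailed study sessions). Assumed: Sessions 3 and 5 fall at the end of each treatment and Session 4 at the end of the washout. No session days are stated, but the 6-week periods and the pill counts at Sessions 3 and 5 point that way.

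**Timeline in weeks.** Session 2 = 0. Session 3 = 0 + 6 = 6. Session 4 = 6 + 2 = 8. Session 5 = 8 + 6 = 14.

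| Session | Week | J-wire, nitroglycerin, laboratory tests | Adverse event questionnaire | Next listed questionnaire |
|---|---|---|---|---|
| 2 | 0 | yes | no | Session 3, 6 weeks later |
| 3 | 6 | yes | yes | Session 5, 14 − 6 = 8 weeks later |
| 4 | 8 | yes | no | Session 5, 6 weeks later |
| 5 | 14 | yes | yes | none |

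**Off-drug intervals.** Each patient has two, one after each treatment: 25 × 2 = 50. Intervals with a questionnaire at their end: 0 of 50. The 25 washout intervals can be reached only through the Session 5 questionnaire, which would have to look back 8 weeks to Session 3. The 25 intervals after Session 5 cannot be reached at all.

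**Procedure days.** 25 × 4 = 100, of which the 25 at Session 5 have no later inquiry.

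**Laboratory values.** Session 4 repeats the metabolic profile and eGFR about 2 weeks off the first drug. Nothing repeats them after Session 5. With 1:1 allocation (assumed; no ratio is stated), resveratrol is the second drug for 12 or 13 of the 25, and those patients have no off-drug eGFR after resveratrol.

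**Illustration of scale.** The event risks here are assumptions. If Session 5 does look back over the washout, off-drug events after resveratrol can be seen only in the 12 or 13 resveratrol-first patients. With follow-up after both treatments they can be seen in all 25.

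- Chance of at least one event = 1 − (1 − p)^n. At p = 5%: 46% (n = 12), 49% (n = 13), 72% (n = 25). At p = 10%: 72%, 75%, 93%.
- One-sided 95% upper bound with zero events = 1 − 0.05^(1/n): 22% (n = 12), 21% (n = 13), 11% (n = 25).

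If Session 5 does not look back, the present number of patients so observed is 0.

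**The case against.** The strongest reply is that silence is not prohibition. The protocol does not exclude follow-up after Session 5, and the consent pages are not available for checking. It would therefore be wrong to infer that late events are never followed; the documents support only that no follow-up is specified. Likewise, Session 5 as the last treatment day is an inference from the 6-week periods, not a stated date.

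A reader might also infer that the whole safety record depends on sequence, because the first drug gets 2 weeks of off-drug observation and the second gets none. The text does not support that for adverse events, since Session 4 has no questionnaire and the washout lacks a dedicated inquiry too. The firm contrast between periods is confined to the repeat laboratory tests.

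A third tempting step is to say that a telephone call would show whether a fall in eGFR at Session 5 reversed. It would not, because a call measures nothing. Reversibility is not a stated aim either, and eGFR is listed among the other measurements. On-treatment change in eGFR is still measured in both periods, from Session 2 to 3 and from Session 4 to 5.

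Two further points stand in part. The 2 weeks are given only to separate the treatments, not as a safety risk window, so using them for follow-up is a convenient choice that matches the two intervals. And the document is dated 23 February 2024, with a statistical section in the past tense that names an R version. This suggests, without proving it, that visits were complete.

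None of this supplies the missing inquiry after Session 5 or at the end of the washout.

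**Conclusion.** The point holds as a gap in safety collection. As written, none of the 50 off-drug intervals has its own adverse event inquiry, and the 25 after Session 5, together with the last of each patient's four procedure days, have no later inquiry at all. Washout events depend on an unstated recall period and may be attributed to the wrong drug.

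The counts rest on all 25 patients completing both periods and on the inferred session timing. The figure of 12 or 13 rests on 1:1 allocation, and the detection chances on assumed risks. The documents identify no specific delayed or withdrawal risk, so this is a modest, inexpensive improvement and not a fatal flaw. The flow-mediated dilation comparison is unaffected.

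**What to change.** 1. At Session 4, add the existing adverse event questionnaire and medication update, covering Session 3 to Session 4.
2. About 2 weeks after Session 5, make one telephone contact using the same questionnaire. The investigator should review the Session 5 laboratory results before the call.
3. Record onset dates, and report events in each off-drug interval under the preceding treatment.
4. State in the report that off-drug eGFR is available only after the first treatment.

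Steps 1 and 2 need to go together: a call alone would give the second treatment a dedicated off-drug inquiry and leave the washout without one.

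The cost is 25 calls by existing staff, a short form at Session 4, a brief amendment, and 2 more weeks in the study per patient. No dose, eligibility criterion, endpoint or efficacy analysis changes.

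If visits are already complete, report adverse events and eGFR by sequence and period, and state the lack of follow-up after Session 5 as a limitation.

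### Adverse events and pill counts are taken once per period, at the post-treatment session, and complete case is undefined, so a patient who stops drug and misses that session can be lost from both safety and efficacy data

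*Combined protocol and SAP*

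**What the plan says.** Study Design sets out a two-period crossover: "25 subjects with stage 3 CKD and diabetes will be randomized to receive either resveratrol first then matching placebo or placebo first then resveratrol". On timing, "The treatment with resveratrol or placebo will be for 6 weeks and separated by a 2 week washout period".

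Detailed study sessions gives the visits. Session 2 takes the pre-treatment measurements and ends with "Start study drug after this visit". The next entry reads "Session 3: will include the same measurements as Session 2", and it adds a physical activity questionnaire, a pill count, a medication update and "Completion of an adverse event questionnaire". For the second period, "Sessions 4 and 5: will involve the exact same procedures as Sessions 2 & 3 above", with the other treatment.

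Statistical analysis specifies a mixed model with condition, time and their interaction, and a random intercept per patient. On missing data it says only this: "A complete case analysis was utilized when analyzing primary and secondary outcomes".

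The documents describe no contact between the two sessions of a period, no assessment at early stopping, no recording of reasons for stopping, no safety set and no adverse event analysis. They do not say what makes a case complete.

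**The concern.** Events that make a patient stop are those a safety record most needs to hold, and here they are solicited only at a session that such a patient may not attend. The same session supplies the period's only post-treatment brachial artery dilation (BA-FMD) value. One missed visit can therefore cost the adverse event, the exposure count and the efficacy change together.

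If stopping is related to treatment, the remaining comparison describes a selected group. In a 25-patient crossover each lost patient is 4% of the sample (1/25). The trial's own tolerability data also matter: judging only by their titles, the two studies cited for the safety of the dose (references 14 and 15) concerned fatty liver disease and type 2 diabetes, not CKD.

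**Working it through.** **Step 1: the schedule.** Placing Sessions 3 and 5 at week 6 of each period is an inference from Study Design and the session list. So is the natural reading that Session 4 mirrors Session 2 and Session 5 mirrors Session 3.

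| Session | Timing | Outcomes | Adverse event questionnaire and pill count |
|---|---|---|---|
| 2 | Before period 1 drug | Yes | No |
| 3 | End of period 1 | Yes | Yes |
| 4 | Before period 2 drug | Yes | No |
| 5 | End of period 2 | Yes | Yes |

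Outcomes are thus measured before and after each treatment. What is missing is any value, or any adverse event question, between the two.

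**Step 2: what is kept, by attendance.**

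| Patient | Adverse event record | Efficacy if sessions are dropped | Efficacy if patients are dropped |
|---|---|---|---|
| Stops drug but attends every session | Both periods | All data | All data |
| Leaves before Session 3 | None | Session 2 only, so no change for either condition | Nothing |
| Misses Session 3, attends 4 and 5 | No period 1 form (Session 5 look-back not stated) | Period 2 change and Session 2 | Nothing |
| Leaves before Session 5 | Period 1 only | Period 1 change and Session 4 | Nothing |

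The last two rows show why the undefined term matters: one reading keeps a full period's change and the other discards it. In the second row, neither reading rescues the patient.

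**Step 3: illustrative size.** The plan gives N = 25 and alpha 0.05 but no dropout rate, effect size, SD or power, so there is no stated figure to reproduce. Let p be the assumed share who stop *and* miss the post-treatment session.

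- Expected number lost: 25p.
- Chance of losing at least one: 1 − (1 − p)^25. At p = 0.04 this is 1 − 0.96^25 = 0.64.
- Power: paired t test (noncentral t), two-sided 0.05 assumed, at the effect that gives 80% power with 25 pairs. That effect is 0.584 SD of the within-patient difference; it is a reference value, not the plan's. Each lost patient removes one pair.
- Bias against all randomized patients: p × g, where g is how much worse the treatment effect is in those lost than in completers. The table uses g = 1 SD; g = 0.5 halves the result and g = 2 doubles it.

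| p | Lost | Chance of at least one | Pairs left | Power | Estimate too favourable by |
|---|---|---|---|---|---|
| 4% | 1 | 64% | 24 | 78% | 0.04 SD |
| 8% | 2 | 88% | 23 | 76% | 0.08 SD |
| 12% | 3 | 96% | 22 | 74% | 0.12 SD |
| 20% | 5 | 99.6% | 20 | 70% | 0.20 SD |

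**Step 4: the safety side at the extreme.** Suppose 5 patients stop resveratrol for side effects, none completes a questionnaire, and the other 20 report nothing. The one-sided 95% upper bound from zero events is 1 − 0.05^(1/20) = 13.9%, while the true proportion is 5/25 = 20%. The record would then exclude the true rate. This shows what the schedule permits; it does not predict what happened.

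**The case against.** Much can be said for the plan. Stopping drug is not the same as missing a visit. Nothing bars a patient who stops from Session 3, or a period 1 stopper from Sessions 4 and 5, and the pill count carries no adherence threshold. A reader might infer that the data come only from patients who tolerated 6 weeks of both treatments, or that an early stop in period 1 forfeits period 2. The documents support neither: attenders are kept, and a period 2 leaver already has a Session 3 adverse event record.

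Nor is the complete-case rule applied to adverse events; it is stated for primary and secondary outcomes. The safety gap comes from the single collection point and the lack of an adverse event analysis. If complete case means dropping single sessions within the mixed model, partial data also survive.

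The point also argues partly from silence. This is a brief protocol for a pilot, and spontaneous reporting may have operated without being described. Consent pages are not in the public text, so an adverse event reporting instruction there cannot be checked. The plan states that recent studies suggest this dose is safe without serious side effects, which may mean few patients stopped.

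These arguments limit the claim to a possibility of unknown frequency. They leave standing that someone who stops and misses the post-treatment session has no described route into that period's adverse event record, and that the analysis rule for such a patient is undefined.

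**Conclusion.** The point holds as a gap in ascertainment and definition, not as a demonstrated loss of patients. It rests on Sessions 3 and 5 falling at the end of treatment and on no other adverse event route existing beyond those described.

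The plausible scale is 1 to 5 of 25 patients, if 4% to 20% stop and do not attend. A statement such as no recorded stops instead of 3 of 25 (12%) would merely restate the assumption that three patients stopped, left and were never recorded; it is not a result. The power and bias figures are conditional in the same way. With a trial this small and the remedy this cheap, the change is worth making.

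**What to change.** 1. When early stopping is reported, complete the existing adverse event questionnaire, the reason for stopping and the pill count by telephone or at drug return.
2. Ask a patient who stops to attend that period's scheduled post-treatment session, and analyse the value under the treatment assigned in that period. This says nothing about whether study drug is taken in the other period, which is not a matter for this review.
3. Fit the planned mixed model to all available sessions rather than only to patients with complete data, and say so in Statistical analysis. This keeps partial data but cannot supply a missing post-treatment value.
4. Report adverse events for everyone who took at least one dose in a period, and withdrawals with reasons by treatment and period.

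The cost is a short paragraph, an occasional telephone call and some dilution of the estimated effect from off-drug values. The document is dated 23 February 2024 and its analysis text is in the past tense, which suggests follow-up may have ended. In that case only steps 3 and 4 apply.
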